#### Aim 2: Non-Inferiority Margins and Power

The non-inferiority margins for this trial were determined in conjunction with a panel of experts on CM+SM and related treatment (the Park-Reeves investigators), our non-physician stakeholder partners, and our patient partners, [name], [name], [name], [name], [name], [name], and [name]. Using a clinical, Delphi-type approach [46] for the complex measure of clinical improvement, the research team agreed upon a non-inferiority margin of no more than 20% lower response for PFD from the PFDD group. The clinical improvement rate for the PFDD group was provided as 78.6% in the Durham study [27]. Thus, with the sample size of 72 subjects per group (after an assumed 2% dropout), we concluded non-inferiority of the PFD to PFDD with a margin of 0.17 units ( $\alpha$ =0.05, 80% power). This corresponds to clinical improvement rate of 61.6% in the PFD group. It was shown in the Durham study that the clinical improvement following PFD was 64.6%.

Determine if PFD provides non-inferior clinical improvement compared to PFDD (Non-inferiority Design)							
Outcome	PFDD	PFD	Data Source	Non-inferiority Margin	α-level	Subjects per group	Power
Clinical Improvement	44/56 (78.6%)	51/79 (64.6%)	Durham [27]	0.17	0.05	72	80%

For these calculations, the drop-out rate is assumed to be 2%, and the one-sided type I error rate is 0.05.

After determination with the Delphi method, the non-inferiority margin was subsequently confirmed as appropriate using Rothman's 95-95 approach [47, 48] and the FDA guidelines for selecting the non-inferiority margin for non-inferiority clinical trials [49]. Using these methods, the non-inferiority margin was estimated using the effect of the standard treatment (PFDD) from Durham's meta-analysis [27], with the lower 1-sided 95% confidence interval for the random-effects meta-analysis calculated to be used as a non-inferiority margin. When the data from the PFDD group from the Durham study was used for the clinical improvement outcome, the 95% lower 1-sided confidence interval from the random effects model was calculated as 0.611. In our proposal, we defined the non-inferiority margin as the difference between the rates. For the clinical improvement outcome, this corresponds to the non-inferiority margin of 0.786 - 0.611 = 0.175 PCORI CER-1503-29700

Version 6 March 01, 2021

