units. Therefore, our recommended non-inferiority margin of 0.17 units, for the clinical improvement outcome, is smaller than the FDA-recommended largest acceptable non-inferiority margin of 0.175 units.

In contrast to clinical improvement, syrinx regression is an objectively measurable and easily quantifiable outcome. It is measured by comparing syrinx size on MRI scans obtained before and after surgery. When the effective sample size is 68 subjects per group, and assuming 89.1% syrinx regression rate in the PFDD group [27], the non-inferiority margin is 0.135 units to reach 81% power. A non-inferiority margin of 0.135 units represents no more than 13.5% reduction from the PFDD group in terms of syrinx regression. Note that a one-sided type I error rate of 0.05 was assumed, and the 'Two group test of equivalence in proportions' option in nQuery Advisor was used.

Determine if PFD provides non-inferior syrinx regression compared to PFDD (Non-inferiority Design)							
Outcome	PFDD	PFD	Data Source	Non-inferiority Margin	α-level	Subjects per group	Power
Syrinx Regression	261/293 (89.1%)	31/38 (81.2%)	Durham [27] and PRSRC	0.135	0.05	72	81%

For these calculations, the drop-out rate is assumed to be 2%, intra-class correlation coefficient is 0.05, and the one-sided type I error rate is 0.05.

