The non-inferiority margins for this trial were determined in conjunction with a panel of experts on CM+SM and related treatment (the Park-Reeves investigators), our non-physician stakeholder partners, and our patient partners, [name], [name], [name], [name], [name], [name], and [name]. Using a clinical, Delphi-type approach [46] for the complex measure of clinical improvement, the research team agreed upon a non-inferiority margin of no more than 20% lower response for PFD from the PFDD group. The clinical improvement rate (the improvement from baseline to 12 months) for the PFDD group was provided as 78.6% in the Durham study [27]. Thus, with the sample size of 72 subjects per group (after an assumed 2% dropout), we can conclude the non-inferiority of the PFD to PFDD with a margin of 0.17 units (α =0.05, 80% power). This corresponds to clinical improvement rate of 61.6% in the PFD group. It was shown in the Durham study that the clinical improvement following PFD was 64.6%.

Determine if PFD provides non-inferior clinical improvement compared to PFDD (Non-inferiority Design)							
Outcome	PFDD	PFD	Data Source	Non-inferiority Margin	α-level	Subjects per group	Power
Clinical Improvement	44/56 (78.6%)	51/79 (64.6%)	Durham [27]	0.17	0.05	72	80%

For these calculations, the drop-out rate is assumed to be 2%, and the one-sided type I error rate is 0.05.

After determination with the Delphi method, the non-inferiority margin was subsequently confirmed as appropriate using Rothman's 95-95 approach [47, 48] and the FDA guidelines for selecting the non-inferiority margin for non-inferiority clinical trials [49]. Using these methods, the non-inferiority margin was estimated using the effect of the standard treatment (PFDD) from Durham's meta-analysis [27], with the lower 1-sided 95% confidence interval for the random-effects meta-analysis calculated to be used as a non-inferiority margin. When the data from the PFDD group from the Durham study was used for the clinical improvement outcome, the 95% lower 1-sided confidence interval from the random effects model was calculated as 0.611. In our proposal, we defined the non-inferiority margin as the difference between the clinical improvement rates in the PFDD and PFD groups ($\pi_{PFDD} - \pi_{PFD}$). For the clinical improvement outcome, this corresponds to the non-inferiority margin of 0.786 – 0.611 = 0.175 units. Therefore, our

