recommended non-inferiority margin of 0.175 units for the clinical improvement outcome is consistent with the FDA-recommended largest acceptable non-inferiority margin of 0.175 units.

In contrast to clinical improvement, syrinx regression is an objectively measurable and easily quantifiable outcome. It is measured by comparing syrinx size on MRI scans obtained before and after surgery. When the effective sample size is 68 subjects per group, and assuming 89.1% syrinx regression rate in the PFDD group [27], the non-inferiority margin is 0.135 units to reach 81% power. A non-inferiority margin of 0.135 units represents no more than 13.5% reduction from the PFDD group in terms of syrinx regression. Note that a one-sided type I error rate of 0.05 was assumed, and the 'Two group test of equivalence in proportions' option in nQuery Advisor was used for the sample size calculations.

Determine if PFD provides non-inferior syrinx regression compared to PFDD (Non-inferiority Design)							
Outcome	PFDD	PFD	Data Source	Non-inferiority Margin	α-level	Subjects per group	Power
Syrinx Regression	261/293 (89.1%)	31/38 (81.2%)	Durham [27] and PRSRC	0.135	0.05	72	81%

For these calculations, the drop-out rate is assumed to be 2%, intra-class correlation coefficient is 0.05, and the onesided type I error rate is 0.05.

Aim 3: Power Calculations

Based on preliminary data using the Chiari Health Index in Pediatrics (CHIP)[50], we observed a 0.12±0.16 unit improvement in Quality of Life (QOL) scores following PFDD. Our sample size of 72/group (effective sample size of 68/group) will provide 82% power to detect a 0.20±0.16 unit improvement in CHIP QOL scores following PFD (α =0.05). Both from an analytical standpoint and from the view of PRSRC investigators and our patient partners, this value represents both a significant and meaningful increase in QOL

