The primary outcome is a binomial outcome measured as a surgical complication and/or requirement for reoperation for complication management ≤ 12 (+/- 2 months) months after initial PFDD or PFD. To account for within cluster correlation, possibly variable cluster size and the relatively small number of clusters in this cluster randomized trial, generalized estimating equations (GEE) with small-sample correction or random effect logistic regression will be used for the primary analysis of this cluster randomized trial [35, 36].

Specifically, a GEE model with a logit link function and adjustment for baseline covariates can be expressed as follows:

$logit(\pi_{ij}) = \mu + \delta T_i + x_{ij}\beta$

where $T_i = I$ if group *i* is assigned PFD and 0 otherwise. Accordingly, δ is the intervention effect. Let x_{ij} is the p-dimensional vector of group-level of individual level covariates from individual *j* (*j* = 1, ..., n_i) nested in center *i* (*i* = 1, ..., # of active centers here); and β is the vector of covariate effects. Also let the outcomes (CSF-related complication ≤ 6 months, yes/no) are independently distributed as $y_{ij} \sim \text{Bernoulli}(\pi_{ij})$. Further let, μ be the log-odds of positive outcome ($y_{ij} = 1$) for PFDD subjects with reference values for covariates ($x_{ij} = 0$) and average random effect ($\gamma_i = 0$). The exchangeable correlation structure will be used for the within-group homogeneity for the correlation structure of the outcomes. Note that, this correlation parameter corresponds to the intraclass correlation coefficient (ICC).

Specific Aim 2:

Hypothesis: Clinical improvement and syrinx regression provided by PFD will be non-inferior compared to those provided by PFDD.

Anticipated Outcome: Clinical symptoms, neurological function, and syrinx regression ≤ 12 months (± 2 months) provided by PFD will be non-inferior compared to those provided by PFDD. The non-inferiority margin is defined as the difference between the outcome rates by treatment. For the clinical improvement outcome, a non-inferiority margin of 0.17 units will be used. A non-inferiority margin of 0.135 units will be used for the syrinx regression outcome.

Clinical symptoms, neurological function, and syrinx regression are defined as rates of change from baseline to 12 months. The 1-sided confidence interval for the difference in rates between the PFD and PFDD groups will be calculated and compared to the corresponding non-inferiority margins.

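### The stated power figures mix original and recalculated assumptions: the syrinx footnote's ICC of 0.05 does not fit its effective n of 68, clinical improvement has no design effect, one SAP sentence gives margin 0.175, and Protocol 9.5 draws 148 patients from a calculation for 216

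*SAP*

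**What the plan says.** **Syrinx regression** (SAP 7.2.1 and Protocol 9.5, Aim 2: Non-Inferiority Margins and Power). Both documents base the 81% power on an effective sample: "When the effective sample size is 68 subjects per group, and assuming 89.1% syrinx regression rate in the PFDD group". The margin is 0.135 and alpha is one-sided 0.05. The table lists 72 per group, and its footnote states: "For these calculations, the drop-out rate is assumed to be 2%, intra-class correlation coefficient is 0.05". Aim 3 also uses an effective 68 per group, for 82% power.

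**Clinical improvement** (same sections). The Protocol reads: "with the sample size of 72 subjects per group (after an assumed 2% dropout), we concluded non-inferiority", with a margin of 0.17, a PFDD rate of 78.6% and 80% power. The SAP uses the same inputs. In neither document does this table's footnote give an ICC or an effective sample size.

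**Margin for clinical improvement.** After computing 0.786 - 0.611 = 0.175, the SAP power section refers to a "recommended non-inferiority margin of 0.175 units for the clinical improvement outcome is consistent with" the largest acceptable value. At the same place the Protocol says "our recommended non-inferiority margin of 0.17 units, for the clinical improvement outcome, is smaller than" that value. SAP 7.5 states the rule: "For the clinical improvement outcome, a non-inferiority margin of 0.17 units will be used".

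**Aim 1 sample size.** The recalculation of November 2017 (both documents) uses ICC 0.01 and cluster size 6, giving a design effect of 1.05. With variable cluster sizes the plan states 1.06. It arrives at 145 evaluable and 148 enrolled for 84% power, which the Protocol treats as a minimum, with up to 238. The Protocol's next paragraph, Aim 1: Power Calculations, starts from 90% power, ICC 0.05 and 36 centers of 6, moves to 48 centers of 6 for dropout, and concludes 148. The SAP's counterpart ends with the original 40 centers and 240 patients.

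**The concern.** The plan was sized once at ICC 0.05 and again at ICC 0.01, and figures from the two rounds now stand side by side. A reader cannot tell which ICC lies behind which power, and the three aims' powers cannot be compared when one is labelled with an ICC it did not use and another ignores clustering. In a non-inferiority comparison the power statement helps the reader judge an inconclusive result. The margin decides the result itself and should have one value throughout the SAP. The Protocol's Aim 1 paragraph, taken alone, says that 148 patients give 90% power for the primary outcome at ICC 0.05.

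**Working it through.** **Formulas.** Non-inferiority power with equal true rates and unpooled variance: SE = sqrt(2p(1-p)/n), power = Phi(margin/SE - 1.645). Design effect: DE = 1 + (m - 1) x ICC for equal clusters, and DE' = 1 + {(cv^2 + 1)m - 1} x ICC for variable clusters; both are in the plan. Effective n = 72/DE. Aim 3: two-sided t-test with standardized difference (0.20 - 0.12)/0.16 = 0.5. Aim 1: two-proportion test with pooled null variance, two-sided alpha 0.05, no continuity correction.

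**1. Syrinx regression (p = 0.891, margin 0.135).**
- Plan's figure: n = 68 gives SE 0.0534, 0.135/0.0534 = 2.526, power Phi(0.881) = 81.1%. The stated 81% reproduces.
- Source of 68: 72/1.05 = 68.6 and 72/1.06 = 67.9, both at ICC 0.01. (The plan's formula with m = 2.9 and cv 1.08 gives 1.053 rather than 1.06, hence 68.4; the inference is the same.)
- At the footnote's ICC: DE = 1 + 5 x 0.05 = 1.25, and 72/1.25 = 57.6.

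If ICC 0.05 were really intended, power would depend on cluster size and cv:

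| m, cv | DE | Effective n | Syrinx | Aim 3 |
|---|---|---|---|---|
| 2.9, equal | 1.095 | 65.8 | 79.9% | 81.2% |
| 6, equal | 1.25 | 57.6 | 75.2% | 75.8% |
| 6, cv 1.08 | 1.60 | 45.0 | 65.9% | 65.0% |

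Aim 3 at n = 68 gives 82.5%, which agrees with the stated 82%.

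**2. Clinical improvement (p = 0.786, margin 0.17).**
- Plan's figure: n = 72 gives SE 0.0684, 0.17/0.0684 = 2.487, power Phi(0.842) = 80.0%. The stated 80% reproduces only with no design effect.
- With DE 1.05 (n = 68.6) power is 78.3%; with n = 68, as used for the other outcomes, it is 78.0%.

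**3. Margin.** Side by side: 0.17 in the SAP power sentence, the SAP power table, SAP 7.5 and the Protocol; 0.175 as the recommended value in one SAP sentence only. At n = 68 a margin of 0.175 would give 80.0%, against 78.0% at 0.17.

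**4. Aim 1 (17.8% vs 2.7%).**
- Recalculation: 145 at DE 1.05 gives 84.1%, and 145/0.98 = 148. The stated 84% reproduces.
- Protocol's Aim 1 power paragraph: 36 x 6 = 216 and 48 x 6 = 288. At DE 1.25, 216 patients give 91.2%, so the 90% claim fits 216. At DE 1.25, 148 patients give 78.0%.
- 148 follows from neither product.

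**The case against.** The strongest reply is that very little moves. If the footnote is the error, 81%, 82% and 84% all stand, and the one stated power that falls does so by about 2 points. That is correct, and it keeps this a matter of correcting text.

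Four stronger readings are tempting and are not supported.

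- *The SAP has two rival decision rules for clinical improvement.* SAP 7.5 says which margin will be used, and it is 0.17. The 0.175 sentence closes a justification and gives no test instruction.
- *The trial was sized wrongly.* The Protocol's recalculation, immediately before the faulty paragraph, derives 148 at 84% power and ICC 0.01, and the SAP sets out the sequence correctly.
- *The syrinx and quality-of-life powers are overstated.* This holds only if ICC 0.05 was intended, and the effective n of 68 points the other way. Even then, with the plan's then-current average cluster of 2.9 and equal sizes, the loss is only 1 point or so.
- *Assuming equal true rates is an error.* It is a common convention for non-inferiority power. The text would be clearer if it said so.

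It can also be said that 78% for clinical improvement borrows an ICC. This stands: the documents give none for that outcome, and with the ICC of 0.000059 observed in the first 47 patients the 80% would be unchanged. The reason to apply 0.01 is consistency with the other calculations, not evidence about this outcome.

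**Conclusion.** The inconsistencies are real and correctable by text.

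- **Syrinx footnote:** ICC 0.05 contradicts the effective n of 68, which belongs to ICC 0.01. The 81% and Aim 3's 82% stand on that reading. If 0.05 is meant, they become about 75% and 76% at m = 6 with equal sizes (about 66-80% and 65-81% over m = 2.9 to 6 and cv 0 to 1.08).
- **Clinical improvement:** 80% becomes about 78% at margin 0.17, assuming that the Aim 1 planning ICC of 0.01 carries over.
- **Margin:** 0.17 is operative, and the 0.175 sentence in the SAP is out of step.
- **Protocol Aim 1 paragraph:** 148 does not follow from its inputs, which would give it about 78% power rather than 90%.

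The Aim 2 figures assume equal true rates. The powers at ICC 0.01 also depend on cluster-size variation: with m = 6 and cv 1.08, DE' is 1.12 and power is about 79% for syrinx, 76% for clinical improvement and 82% for Aim 1 (145 evaluable). That does not alter which ICC the stated figures used.

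**What to change.** 1. In both documents, change the syrinx footnote to ICC 0.01 and leave 81% and 82% as they are. If 0.05 is intended, restate them as about 75% and 76% (m = 6, equal sizes) and give the cluster size and cv used.
2. For clinical improvement, apply the same planning design effect, say that ICC 0.01 is carried over from Aim 1 because no estimate for this outcome is given, and restate power as about 78% at margin 0.17.
3. In the SAP power section, make 0.17 the chosen margin and 0.175 only the largest acceptable value, as in the Protocol.
4. In the Protocol's Aim 1: Power Calculations, tie the 90% calculation at ICC 0.05 to the original plan, as the SAP does, and give 148 (the minimum, up to 238) its recalculated power of about 84% at ICC 0.01.

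A sentence saying that the Aim 2 powers assume equal true rates would help. The cost is editing two documents. The planned sample size, the tests and the operative margin stay as they are.

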7.3 Interim analyses and Stopping Rules

The Posterior Fossa Decompression with or without Duraplasty for Chiari type I Malformation with Syringomyelia study will appoint an independent Data Safety Monitoring Board (DSMB) of members. The DSMB will meet once prior to the start of the study, and will approve the final protocol prior to its implementation. Additionally, the DSMB will establish a charter to guide its function. The charter would include rules of procedure, definitions of a meeting quorum, and information about meeting logistics.

The purpose of the DSMB is to advise PCORI, the Principal Investigator ([name]), and the Investigators Committee regarding the continuing safety of study participants and the continuing validity and scientific merit of the study. The DSMB is responsible for monitoring accrual of study subjects, adherence to the study protocol, assessment of data quality, performance of individual clinical sites, review of serious adverse events and other subject safety issues, and review of formal interim statistical analyses of treatment efficacy. The DCC will send reports relating to these topics to DSMB members 10 days prior to each DSMB meeting. Based on prospectively defined guidelines to be outlined in the DSMB charter, the DSMB should recommend whether or not to terminate enrollment in the *Posterior Fossa Decompression with or without Duraplasty for Chiari type I Malformation with Syringomyelia* study because of potential safety concerns or high evidence of efficacy. The DSMB will also

have the option to recommend stopping the study due to low likelihood of finding an effect if the trial continues (futility), or if the risks/benefit ratio is not favorable. Each DSMB meeting will result in a summary report that will be provided to the Investigator Committee, PCORI, and each local IRB.

7.4 Outcomes

The goal of this study is to supply patients and families with the information about the risks and benefits of PFDD and PFD that *they feel* are most important in making informed clinical decisions. As such, the primary outcome of interest is reduction in harm to patients, measured as surgical complications and/or requirement for reoperation for complication management ≤ 12 (+/- 2 months) months after initial PFDD or PFD. Complications and reoperation are associated with additional pain as well as emotional and psychological stress, longer hospital stays, and lost time from school/work. Secondary outcomes focus on efficacy outcomes and will include: 1) comparison of pre-operative symptoms and neurological deficits at ≤ 6 weeks, 3-6 months, and 12 (+/- 2 months) months after surgery and syrinx size and spinal alignment (coronal and sagittal Cobb angles) at 12 (+/- 2 months) months after surgery. This outcome will be evaluated using the CHIP and the HUI-3 QOL instruments where analyses based on CHIP will be used as the primary results for aim 3 in case CHIP and HUI-3 results do not agree.

Because this is a surgical trial, an Adjudication Committee, consisting of two pediatric neurosurgeons and one pediatric neuroradiologist independent of the design and conduct of the trial, will adjudicate the primary outcome measure. The committee will review the primary endpoint based on a blinded review of clinical notes, data forms and imaging studies. Decisions by the adjudication committee will determine final outcomes. Consensus definitions of CSF-related complications following neurosurgery have been developed [34]. These definitions have been reviewed and approved by the neurosurgeons participating in the study and will be used in this trial. Likewise, the extent of syrinx resolution following surgery will be determined by centralized review of blinded imaging studies. By contrast, treatment failure (i.e. need for revision PFDD or PFD) will be determined individually by the treating surgeon in consultation with the patient/family, since such decisions are inherently subjective and based both on the surgeon's level of concern and the patient's discomfort and relative acceptance to the inherent risks of surgery (either PFD or PFDD).

7.5 Data Analyses

A Priori Plans for Data Analysis

Descriptive Statistics

Using CONSORT guidelines for cluster-randomized trials,53 We will present descriptive statistics, for continuous variables the mean (+/-standard deviation) or median (minimum, maximum) values and for categorical variables the frequencies and proportion for each cluster. These presentations will be carried out at baseline and at 12-month follow-up. We will provide reasons for dropouts.

Final Comparative Analysis PCORI CER-1503-29700 Based on Protocol Version 6 March, 2021 *Planned sensitivity analyses to determine the impact of key assumptions.* Due to the fact that each patient in a given center will be assigned to the same procedure, it is possible to observe unequal overall sample sizes for each procedure. The initial analysis plan is to give equal weights to all clusters. If there is imbalance in the prognostic factors, we will use weighted analyses where the cluster-level summary score is weighted inversely proportional to the reciprocal of its estimated variance.

Initial analysis will be conducted using per Treatment group assignment prior to adjudication, as it aligns more to in-practice clinical procedures. Sensitivity analyses will be conducted based upon Intent-to-Treat (ITT) (as randomized), and per Protocol (actual treatment) grouping definitions, both pre and post adjudication. Patients with a second Chiari surgery will be analyzed in two different ways in sensitivity analysis, one including vs one excluding second surgeries. and will be.

Comparison methods

Specific Aim 1: Hypothesis: PFD will be associated with fewer surgical complications and less potential harm to patients than PFDD.

Anticipated Outcome: Cerebrospinal fluid (CSF)-related complications ≤ 6 months (e.g. CSF leak, pseudomeningocele, aseptic meningitis, infection, hydrocephalus), and the requirement for additional surgery for wound revision or CSF diversion will be lower after PFD compared with PFDD.

The primary outcome is a binomial outcome measured as a surgical complication and/or requirement for reoperation for complication management ≤ 12 (+/- 2 months) months after initial PFDD or PFD. To account for within cluster correlation, possibly variable cluster size and the relatively small number of clusters in this cluster randomized trial, generalized estimating equations (GEE) with small-sample correction or random effect logistic regression will be used for the primary analysis of this cluster randomized trial [35, 36].

Specifically, a GEE model with a logit link function and adjustment for baseline covariates can be expressed as follows:

$logit(\pi_{ij}) = \mu + \delta T_i + x_{ij}\beta$

where $T_i = I$ if group *i* is assigned PFD and 0 otherwise. Accordingly, δ is the intervention effect. Let x_{ij} is the p-dimensional vector of group-level of individual level covariates from individual *j* (*j* = 1, ..., n_i) nested in center *i* (*i* = 1, ..., # of active centers here); and β is the vector of covariate effects. Also let the outcomes (CSF-related complication ≤ 6 months, yes/no) are independently distributed as $y_{ij} \sim \text{Bernoulli}(\pi_{ij})$. Further let, μ be the log-odds of positive outcome ($y_{ij} = 1$) for PFDD subjects with reference values for covariates ($x_{ij} = 0$) and average random effect ($\gamma_i = 0$). The exchangeable correlation structure will be used for the within-group homogeneity for the correlation structure of the outcomes. Note that, this correlation parameter corresponds to the intraclass correlation coefficient (ICC).

Specific Aim 2:

Hypothesis: Clinical improvement and syrinx regression provided by PFD will be non-inferior compared to those provided by PFDD.

Anticipated Outcome: Clinical symptoms, neurological function, and syrinx regression ≤ 12 months (± 2 months) provided by PFD will be non-inferior compared to those provided by PFDD. The non-inferiority margin is defined as the difference between the outcome rates by treatment. For the clinical improvement outcome, a non-inferiority margin of 0.17 units will be used. A non-inferiority margin of 0.135 units will be used for the syrinx regression outcome.

Clinical symptoms, neurological function, and syrinx regression are defined as rates of change from baseline to 12 months. The 1-sided confidence interval for the difference in rates between the PFD and PFDD groups will be calculated and compared to the corresponding non-inferiority margins.

Second Chiari surgeries will be analyzed as 1) the proportion requiring a surgical revision and 2) the type of second surgery performed (same or cross-over). The 1-sided confidence interval for the difference in rates between the PFD and PFDD groups will be calculated and compared to the corresponding non-inferiority margins.

Specific Aim 3:

Hypothesis: With fewer surgical complications, PFD will be associated with superior QOL compared with PFDD.

Anticipated Outcome: PFD will have superior QOL and will show improvements in overall QOL over time (≤ 12 months post-operatively (± 2 months)) compared to PFDD. In particular, both physical metrics (evaluated by pain frequency, pain severity and non-pain symptoms) and psychosocial metrics will improve at a higher rate and in a shorter period of time after PFD compared to PFDD.

Secondary outcomes include Treatment Efficacy variables and Quality of Life variables. Continuous variables measured at 3 time points over the 12-month follow-up will be analyzed using longitudinal analysis with linear mixed models including the random cluster effect. Binomial and ordinal data will be analyzed using Mixed Model methods accounting for cluster. In addition, sensitivity analyses will be conducted where the missing data points will be imputed based on the last observation carried forward.

It should be noted that for Aim 3, primary analyses will be based on the QoL exam performed at 10 to 14-month window. A sensitivity analyses will also be performed based on the last QoL exam available at any time \geq 3 months after surgery. Analyses based on the mixed effect model will also be performed where both cluster effect and error terms will be random.

Missing data: Based on PRSRC data and early data from this trial, loss to follow-up rate is expected to be low (<2%). To prevent missing data, we will meet with patients at 1 month, 3-6 months and at 12+/-2 months after the procedure. Every effort, including phone call reminders to patients, will be made to decrease loss to follow-up. Loss to follow-up, missing data, and the reasons leading to loss of follow-up or data will be recorded. In case of missing data, we will impute missing data using different methods. Because of the repeated measures nature of the data, the 'last observation

carried forward' method will be utilized [37]. In addition, Buck's method, which is the extended version of regression imputation, will be used [38]. The Buck's imputation will be based on the observed values of patient's age, CM (\geq 5mm tonsillar ectopia), syrinx diameter, and pre-operative comorbidities. In addition to the overall rates of missing data for each procedure, because of the cluster randomized trial, we will also monitor the missing data within each cluster and center and report the discrepancy between the loss to follow-up rates for each procedure. Special attention will be given and separately reported if the entire cluster is loss to follow-up. As a sensitivity analysis for the missing data, study results will be compared for the following three conditions: 1) patients with missing primary outcome variable are excluded from analyses; 2) results with last observation carried forward, and 3) results with Buck's method. Robustness of the results under each scenario will be assessed.

Heterogeneity of Treatment Effect (HTE): As an exploratory analyses, to assess if the procedure is most beneficial for a specific subgroup, the heterogeneity of the effect of performing PFDD vs PFD will be assessed within the following pre-determined subgroups based on: 1) patient age at the time of surgery (<5 years, 5-12 years, 13-18 years); 2) CM status (5-12 mm tonsillar ectopia, >12 mm tonsillar ectopia) [39]; 3) syrinx diameter (3-6 mm, 7-9 mm); and 4) preoperative hydrocephalus or neuromuscular disease, two comorbidities associated with increased morbidity following pediatric CM +/- SM surgery [40]. Demographic and comorbidity data will be collected by trained study research assistants/coordinators with strict oversight by site investigators using standard data collection forms. For HTE analysis, the test of procedure (PFD vs PFDD) by subgroup effect (such as age) interaction will be performed to assess the homogeneity of the procedure effect within each subgroup. All pre-specified subgroup analyses (patient's age, CM status, syrinx diameter, comorbidity, and surgeons' experience) will be reported regardless of observing a statistically significant or not-significant effect.

Sub-analysis by Syrinx size (3-6 mm, 7-9 mm): A planned subgroup analysis for each of the 3 to 6 mm and 7 to 9 mm syrinx diameters will be performed for each of the 3 aims. The test of interaction will be used to assess if the treatment effect is homogeneous within each of the syrinx size subgroups (3- 6 mm vs 7-9 mm). If the test of interaction indicates heterogeneity, using the whole 3 to 9 mm syrinx diameter range, analyses will be performed, to identify, if any, a cut-off point to propose using one surgical method over the other. For example, whether the PFD is associated with greatly fewer surgical complications when the syrinx diameter is less than 5mm, but surgical complication rates are similar for PFD and PFDD when the syrinx diameter is \geq 6 mm will be examined.

Secondary Analysis

The aims will be evaluated using the overall population who were followed from 6 months to 24 months after enrollment. Analysis will be performed to compare the per Treatment groups for time to last follow-up in order to determine if there is differential follow-up times between groups. Analysis of Aims 2 and 3 will be similar to the primary analysis with adjustment for time to last follow-up as a covariate.

Aim 3 includes some questions that may not be applicable for younger children. For example, keeping up with schoolwork or difficulty with math. Therefore, for this ,a subgroup analysis for

those children age >5 years will also be performed. Additional analysis will include subdomain comparisons of: Pain symptoms Headache Back pain Non-pain symptoms Difficulty raising arms Difficulty walking Frequently lose balance Psychosocial Tired Easily frustrated Trouble sleeping Difficulty concentrating Difficulty paying attention in class Forgetful Difficulty with reading Difficulty with math Difficulty learning new things Difficulty keeping up with schoolwork. Covariates in this analysis will include medical history (Autism, ADHD, Known Psych Disease),

pathology (known Craniofacial Anomalies, Known Skull Malformation, Known Hydrocephalus, Known Spine Column Disorder) and Syrinx (Syrinx Level Known, Syrinx AP Diameter).

Exploratory Analysis

Additional exploratory subgroup analyses will be performed for Aims 2 and 3. These analyses will include age (<5,5-12,13-18), CM status (5-12,>12 mm), and preoperative hydrocephalus or neuromuscular disease. These analyses will examine if there is differential response between the groups.

A model of response will also be performed with the additional covariates: parents education, gender, race, insurance, treatment complications, pain, headache, childhood history, hydrocephalus, skull formation, spinal column disorder, syrinx level, syrinx AP diameter, and improved syrinx size.

